9.3 Selection of study population

9.3.1 Recruitment

The clinical part of the recruitment will be conducted by Clinical Trial Center (CTC) located at the Sahlgrenska University Hospital in Gothenburg, Sweden. This centre has helped recruiting the same category of volunteers, as will be recruited for the non-inferiority bridging study, for all previous studies of ETVAX® in Swedish adult volunteers [11, 12, 31].

Previous experience indicate that the number of recruited subjects should not be a problem, and the historical drop-out rate has been low (less than 5%) [12]. The compliance is also expected to be excellent, based on previous experience. However, due to the ongoing COVID-19 epidemic, a higher drop-out rate is expected (estimation 10%), since even mild symptoms may prevent study visits (See section 9.4.3)

9.3.2 Number of subjects

A total number of 126 subjects needs to be included in each arm of the study in order to achieve 90% power to assess the primary objective. Assuming a 10% dropout rate the target number of subjects to be recruited per study arm is therefore 140.

9.3.3 Screening and enrolment log

The clinic will keep a log of all subjects screened and included. The reason for screen failure should be stated for all subjects screened but not included. The reason for withdrawal should be stated for all subjects included but not completed.

Subjects who have signed the ICF will be assigned a screening number. Subjects included will be assigned a subject number.

9.3.4 Inclusion criteria

For inclusion in the study, subjects must fulfil all the following criteria:

1. Male or female aged 18-50 years, inclusive at the time of signing the informed consent.
2. Healthy constitution as established by medical history and physical examination.
3. Willing and able to give written informed consent for participation in the study.
4. Able to comply with study activities, as judged by the Investigator.
5. Female Participants:
 - Women of child-bearing potential (for definition see Section 9.3.6):
 - Have to agree to use an acceptable birth control method during participation in the investigation (see Section 9.3.6).

- A negative pregnancy test (beta human chorionic gonadotropin dipstick test in urine) at Visit 2/Day 1 will be required.

6. Male Participants:

- Have to agree to remain abstinent (refrain from heterosexual intercourse) or use a condom, and agreement to refrain from donating sperm, as defined in Section 9.3.6

In order to receive Dose 2, subjects must fulfil all the criteria above.

9.3.5 Exclusion criteria

Subjects must not enter the study if any of the following exclusion criteria are fulfilled:

1. An acute or chronic medical condition that, in the opinion of the investigator/physician, would render ingestion of the investigational products unsafe or would interfere with the evaluation of responses. This includes, but is not limited to gastrointestinal diseases, and autoimmune diseases.
2. Current malignancy or history of malignancy during the last five years, based on anamnesis.
3. Gastroenteritis within two weeks prior to vaccination.
4. Regular use of laxatives, antacids or other agents that lower stomach acidity.
5. Any planned major surgery during the duration of the study.
6. After 10 minutes supine rest, any vital signs outside the following ranges:
 - Systolic BP > 160 mm Hg
 - Diastolic BP > 100 mm Hg
 - Heart rate < 40 or >85 beats per minute
7. Antibiotic therapy within two weeks prior to the vaccination.
8. Known Hepatitis A, B, C, and/or HIV infection.
9. Concomitant intake of immunomodulating drugs during the study period or less than 3 months prior to the first immunization, with the following exceptions: oral anti-histamines are not allowed during the study period or less than 3 weeks prior to the first immunization. Local anti-histamine treatment is allowed during the study period.
10. Any other significant medical conditions (e.g. poorly controlled psychiatric condition) judged by the Investigator to preclude entry.
11. Intends to receive any other vaccine during the study period, or within two weeks prior to trial vaccination.
12. Has previously received Dukoral or any type of ETEC or cholera vaccines.
13. Brought up in ETEC-endemic areas (e.g., urban and rural areas of Central and South America, Caribbean, most countries in Asia, Africa, etc.).
14. Has travelled to ETEC-endemic areas within the last 3 years OR spent > two months in ETEC endemic areas during the last 10 years.
15. Intends to travel to ETEC endemic countries during the study period.
16. Known or suspected history of drug, chemical or alcohol abuse, as deemed by the investigator/physician.

17. History of severe allergy/hypersensitivity or ongoing allergy/hypersensitivity, as judged by the Investigator, or history of hypersensitivity to drugs with a similar chemical structure or class to ETVAX®.
18. Participation in any other clinical study that included drug treatment with the last administration within the past 3 months prior to administration of study treatment in this study. Patients consented and screened but not dosed in previous clinical studies are not excluded.
19. Concomitant participation in any other clinical study.
20. Females who are pregnant as determined by urine test at inclusion and prior to each vaccination.
21. Females who are nursing.
22. Unable to participate in all study visits.
23. Any condition or circumstance which would make the subject unsuitable for participation in the study in the opinion of the investigator/physician.

In order to receive Dose 2, subjects must not fulfil any of the above criteria.

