7.3.2 Risks

Based on experiences from previous studies with ETVAX[®], immunization is expected to give rise to only a low frequency of mild and transient symptoms, including a few loose stools, mild nausea/vomiting, and abdominal pain or bloating. In the previous trial including 129 Swedish adults there were no significant differences in either frequency or severity of AEs between the study groups receiving ETEC vaccine with or without dmLT and the placebo group receiving bicarbonate buffer alone [12]. The excellent safety profile of the vaccine was supported by very few recorded AEs in Bangladeshi adults vaccinated with ETEC vaccine

with or without 10 µg dmLT, with no significant differences between subjects in the vaccine (n=30) or placebo groups (n=15) [14]. In the recent clinical trial in Finland (OEV-123), no significant differences in AEs were recorded between subjects receiving ETVAX[®] (n=374) and placebo recipients (n=375).

Since the new partially dried vaccine formulation contains the same vaccine components as the previously tested wet vaccine formulation, the risk of inducing different vaccine associated AEs in subjects receiving the new formulation is deemed to be low.

Blood sampling of study participants may cause some pain at the time of sample collection and may result in the development of a bruise but has no other risks.

The risk for individuals participating in this study is therefore assessed to be very small.

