8.2.1 Secondary endpoints

Occurrence of solicited symptoms for six days after each vaccination (day of vaccination and five subsequent days).

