For the exploratory analyses, subgroups of subjects in the main study ($n=20-40$, evenly distributed between the two treatment arms) will participate in extra follow-up visits 5 ± 1 (Visit 3b, $n=40$), 30 ± 7 (Visit 4b, $n=20$) and 75-125 (Visit 4c, $n=20$) days after the second

dose in addition to the regular visits (Visit 1-4) in the main study. Blood samples will be collected on all exploratory visits. The extra visits and analyses for exploratory analyses may continue after the main part of the study has been completed and the database locked.

For subjects participating in main study, the total volume of blood drawn will not exceed 40 ml. For subjects also participating in the exploratory analyses, the total volume will not exceed 250 ml.

The timing and frequency of study visits and assessments in each study part are presented in the schedules of events in Table 9.1 and 9.2.

Table 9.1 Schedule of events – Main Study assessments

	Visit 1 Screening	Visit 2 Dose 1	Visit 3 Dose 2	Visit 4 Follow-up
Day/assessments	Day -30 to Day 1 ^a	Day 1 ^a	Day 15 ^b (±2 days)	7 days (6-10 days) after Dose 2
Informed consent	X			
Demographics and relevant medical/surgical history	X			
Inclusion/exclusion criteria	X	X	X	
Physical examination	X			X
Vital signs (Blood pressure and Heart rate)	X			X
Vital signs (Body temperature)	X	X	X	X
Pregnancy Test (Urine)	X	X	X	
Randomization		X		
Dosing		X	X	
Blood sampling for immunology (primary endpoint)		X		X
Subject diary distribution		X	X	
Subject diary collection			X	X
Baseline events	X ^c	X ^c		
Adverse Event and Serious Adverse Event reporting		X	X	X
Prior and concomitant medications	X	X	X	X

^aScreening visit and Day 1 (Visit 2) may be performed on the same day.

^bIf a subject is unable to come for the visit on day 15±2 due to *e.g.* illness or rules regarding quarantine due to the COVID-19 epidemic, the second vaccine dose can be administered up to 28 days after the first dose.

^cUntil subject receives IMP

Table 9.2 Schedule of events – Main and Exploratory Study assessments

	Visit 1 Screening	Visit 2 Dose 1	Visit 3 Dose 2	Visit 3b Exploratory	Visit 4 ^c Follow-up	Visit 4b Exploratory	Visit 4c Exploratory
Day/assessments	Day -30 to Day 1 ^a	Day 1 ^a	Day 15 ^b (±2 days)	5 ±1 day after Dose 2	7 day (6-10 days) after Dose 2	30 ±7 days after Dose 2	75-125 days after Dose 2
Informed consent	X						
Demographics and relevant medical/surgical history	X						
Inclusion/exclusion criteria	X	X	X				

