9.5.4.3 Subject Diary

The study diaries will contain questions regarding adverse events and current medication. The adverse event and medication diaries should be filled in by the subjects on the day of vaccination and five subsequent days. Information about adverse events and medication obtained from the diaries will be verified by interviewing the subject at the following clinic visit and will then be registered in the CRFs by the study nurse/physician, i.e data from study diaries will not be transcribed word by word into the eCRF.

The following solicited AEs will be included in the diary: fever, nausea, vomiting, abdominal pain and loose stools/diarrhea.

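### Can a gastrointestinal reaction to Dose 1 bar Dose 2 and so bias the primary non-inferiority comparison?

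*Combined protocol and SAP*

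**What the plan says.** Section 9.3.5 lists 23 exclusion criteria and then adds "In order to receive Dose 2, subjects must not fulfil any of the above criteria". Criterion 3 is "Gastroenteritis within two weeks prior to vaccination". Unlike criterion 9, it is not tied to the first immunization, so it is among the items checked again at Dose 2. Table 9.1 schedules an eligibility check at Visit 3, the same visit as the first "Subject diary collection".

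Section 9.5.4.3 states: "The following solicited AEs will be included in the diary: fever, nausea, vomiting, abdominal pain and loose stools/diarrhea". Section 7.3.2 expects a low frequency of mild, transient effects, "including a few loose stools, mild nausea/vomiting, and abdominal pain or bloating".

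Dose 2 is planned for Day 15 ±2. Footnote b of Table 9.1 extends this to 28 days after Dose 1 for a subject "unable to come for the visit on day 15±2", with illness among the examples.

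Section 9.5.2.1 takes the endpoint titer from the sample drawn 7 days after the second vaccination. The primary analysis uses the PPAS, which needs evaluable efficacy data (9.7.4.2). The FAS needs available data (9.7.4.1). Dropouts and missing data are left to a separate SAP (9.7.5.2), whose text is not in the document reviewed.

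**The concern.** The two-week look-back is almost as long as the dose interval. A subject with vomiting and loose stools after Dose 1 could be judged at Visit 3 to have had gastroenteritis. The protocol does not define the term or say whether a vaccine reaction counts. Nor does it say whether a subject who attends but fails a time-limited criterion may use the later dosing window.

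If Dose 2 were then withheld, no endpoint exists in the form that section 9.5.2.1 defines. The subject could drop out of the PPAS and perhaps the FAS as well. Inclusion in the primary analysis would then depend on a post-randomization event that is itself the secondary endpoint: "Occurrence of solicited symptoms for six days after each vaccination (day of vaccination and five subsequent days". If the formulations differed in gastrointestinal tolerability, and subjects who react also respond differently, the seroconversion difference would be biased and the FAS might not reveal it.

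**Working it through.** **The plan's own figure.** Inputs from section 9.7.4.3: 85% response in both arms, margin 0.15, two-sided 95% interval, 90% power, Farrington-Manning method. The restricted estimates under a difference of -0.15 are 0.7489 and 0.8989.

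- Null variance: 0.7489 × 0.2511 + 0.8989 × 0.1011 = 0.279 (root 0.528).
- Alternative variance: 2 × 0.85 × 0.15 = 0.255 (root 0.505).
- n = (1.960 × 0.528 + 1.282 × 0.505)² / 0.15² = 125.8, so 126 per arm. Then 126 / 0.90 = 140.

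The stated 126 and 140 reproduce and do not depend on this point.

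**How far the look-back reaches.** With Dose 2 on Day D, diary day j (1 to 6) falls inside it if D − j ≤ 14.

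- D = 13, 14 or 15: Days 1-6.
- D = 16: Days 2-6.
- D = 17: Days 3-6.
- D = 21 or later: no diary day.

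The 28-day limit is Day 29. A reaction confined to the diary period is therefore outside the look-back from Day 21 to Day 29, inside the permitted interval.

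**Effect on the error rate if Dose 2 is lost.** The documents give no rate of such losses, so the counts are assumptions. Take true rates among all treated of 70% (dried) and 85% (wet), with 126 per arm. If k dried-arm subjects with response rate r are lost, the remaining dried rate is (0.70 × 126 − r·k) / (126 − k). For r = 0 and k = 6 this is 88.2 / 120 = 0.735. The table gives the exact binomial probability that the planned normal-approximation lower limit is at or above -0.15. With no loss it is 2.6%.

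| Response rate of those lost, dried arm only | k = 2 | k = 4 | k = 6 |
|---|---|---|---|
| 0% | 4.2% | 6.8% | 10.3% |
| 35% | 3.3% | 4.3% | 5.4% |
| 50% | 2.9% | 3.5% | 4.0% |
| 70% (same as the arm) | 2.6% | 2.6% | 2.6% |
| 0%, equal loss in both arms | 2.3% | 2.1% | 1.9% |

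In the other direction, with true rates of 85% in both arms and non-responders lost from the wet arm only, power falls from 91.7% to 86.6%, 79.9% and 71.8%.

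**Single-trial example.** Wet 107/126 against dried 99/126 gives a difference of -6.3 points and a lower limit of -15.9%, a failure. With two dried non-responders absent, 99/124 gives -5.1 points and -14.5%, a pass.

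**Would the obvious sensitivity analysis help?** Counting everyone without a result as a non-responder multiplies both rates by (1 − f), where f is the missing fraction. A true gap of 15 points shrinks to 14.25 points at f = 5% and 13.5 points at f = 10%. With 140 per arm, true rates 70% and 85%, and equal random missingness, false non-inferiority is 3.5% at 5% missing and 4.6% at 10%, against 2.6% with none missing. Power at 85% in both arms is 89.1% and 84.4%.

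**The case for a change.** The best case for a change is that an undefined word can decide who enters the primary analysis. The 10% dropout allowance protects power but not against unequal loss. Section 7.3.2 judges different adverse events unlikely, "Since the new partially dried vaccine formulation contains the same vaccine components as the previously tested wet vaccine formulation". Yet the new sachet weighs 10.84 g against 5.6 g (10.84 / 5.6 = 1.94-fold), and tolerability of the new formulation is the secondary objective. The cited trials with no significant adverse event differences from placebo did not test the dried formulation. A wording edit, a table and a sensitivity analysis would be cheap.

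The silence in the text is real, and so is the arithmetic. The chain from one to the other is not established:

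- Criterion 3 names a diagnosis, while sections 7.3.2 and 9.5.4.3 list symptoms. No passage equates the two.
- The closing sentence cannot be meant item by item. Criterion 12, taken literally at Dose 2, would exclude everyone who had Dose 1. Criterion 6 uses blood pressure and heart rate that Table 9.1 does not schedule at Visit 3. These are drafting slips, and they show that the sentence already has to be read with judgment.
- Delay is at least as plausible as loss, and the loss scenarios above allow for none.
- Removal from both analysis sets is an inference. Section 9.3.7.1 asks for withdrawal assessments, preferably on the final-visit scheme, and Visit 4 includes the endpoint blood sample. Neither set definition names two doses.
- Staff caring for subjects are blinded (9.4.6), so a judgment about criterion 3 cannot follow known allocation. It could still follow a true difference in reactions.
- Total sachet weight says little about tolerability, and the composition table in 9.4.1.11 is redacted.

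The proposed steps also gain little. A rule fixed only before unblinding comes after database lock (9.4.6), when every Dose 2 decision has been made. Non-responder imputation is anti-conservative under equal missingness, as shown above. Reasons for withdrawal are already logged (9.3.3) and doses given are recorded per subject (9.4.4), so missed second doses can be counted by arm and reason.

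**Conclusion.** No change to the plan is needed. Sections 9.3.5 and 9.5.4.3 and footnote b of Table 9.1 leave open how a gastrointestinal symptom after Dose 1 bears on criterion 3 and on the timing of Dose 2. That is a missing detail of the kind investigators settle in practice. How it is settled is a clinical matter for the sponsor and investigator, and I take no position on it.

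Bias in the primary comparison needs three things together: Dose 2 forfeited rather than delayed, forfeited unequally between arms, and forfeited by subjects whose response differs from the rest of their arm. The documents supply none of these inputs. The 4.2-10.3% error rates also assume that every lost subject is a non-responder from the dried arm and that the true difference lies exactly at the margin. Without the link to response, the rate stays near the planned 2.6%. The concern describes a possible mechanism and does not show a defect. If the study report showed an appreciable arm imbalance in missed second doses for gastrointestinal reasons, the primary result would need to be read with that in mind.

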9.3.6 Restrictions

The following restriction must be respected by the study subjects during participation in the study:

- Contraception (Women): A woman is considered of childbearing potential (WOCBP), i.e. fertile, following menarche and until becoming post-menopausal unless permanently sterile. Permanent sterilisation methods include hysterectomy, bilateral salpingectomy and bilateral oophorectomy. A postmenopausal state is defined as no menses for 12 months without an alternative medical cause.

A WOCBP can participate in the study if practising abstinence (only allowed when this is the preferred and usual lifestyle of the subject)

OR

is willing to use a highly effective method of contraception with a failure rate of < 1% to prevent pregnancy (from at least 4 weeks prior to dose until completion of the main study, i.e. the follow-up visit 7 days after the last dose):

- combined (oestrogen and progestogen containing) hormonal contraception associated with inhibition of ovulation (oral, intravaginal, transdermal)
 - progestogen-only hormonal contraception associated with inhibition of ovulation (oral, injectable, implantable), intrauterine device (IUD)
 - intrauterine hormone-releasing system (IUS)
- Contraception (Men):

- With a female partner of childbearing potential or pregnant female partner, men must remain abstinent or use a condom during the treatment period and 7 days after the final dose of IMP. Men must refrain from donating sperm during the same period. Periodic abstinence (e.g. calendar, ovulation, symptothermal or postovulation methods) and withdrawal are not adequate methods for preventing drug exposure.
- Blood donation: The subjects participating in the main study must not donate blood or plasma during the study until 1 month after the last visit. The subjects participating in the exploratory study must not donate blood or plasma during the study until 3 months after the last visit.
- Fasting: The subject should not eat or drink for at least one hour before or after ingestion of the study vaccine

9.3.7 Removal of subjects from therapy or assessment

9.3.7.1 Subject withdrawal criteria and replacement

A study subject should be withdrawn from the study treatment if, in the opinion of the Investigator, it is medically necessary, or if it is the expressed wish of the subject.

Irrespective of the reason for withdrawal and whenever possible, the subject should be examined. Relevant laboratory test samples should be obtained, and all relevant assessments should be completed, preferably according to the scheme for the final assessment. The CRF should be completed as far as possible and checked/verified by the Monitor.

Subjects may be discontinued from the investigation at any time at the discretion of the Investigator for any of the following reasons:

- Severe non-compliance to the Study Protocol procedures, as judged by the Investigator and/or SBH
- Subject is lost to follow-up
- Significant AEs posing a risk for the subject, as judged by the Investigator and/or SBH

A withdrawn subject is not allowed to re-enter into the trial.

9.4 Treatments

The wet formulation consists of a liquid suspension of inactivated bacteria (ETEX 21-24) and LCTBA in one vial, freeze-dried dmLT adjuvant in a second vial, and effervescent buffer granules in a separate sachet. Prior to administration, the buffer is dissolved in 150 ml tap water, followed by the addition of the content of the vaccine vial (inactivated bacteria mixed with LCTBA) and reconstituted and diluted adjuvant dmLT from the second vial.

In the partially dried formulation, dmLT and LCTBA are spray-dried and mixed with the buffer granules and stabilizing excipients in a sachet. Prior to administration, the content of the buffer sachet (buffer, dmLT, and LCTBA) is dissolved in 150 ml tap water, followed by the addition of a liquid suspension of inactivated bacteria (ETEX 21-24).

The identity of the different components of the two vaccine formulations are described below.

9.4.1 Identity of Investigational Medicinal Product (IMP)

9.4.1.1 Inactivated *E. coli* ETEX 21

The *E. coli* ETEX 21 strain was developed using a recombinant plasmid expressing the entire CFA/I operon

[REDACTED]

9.4.1.2 Inactivated *E. coli* ETEX 22

The *E. coli* ETEX 22 strain was developed using a recombinant plasmid expressing the entire CS3 operon

[REDACTED]

9.4.1.3 Inactivated *E. coli* ETEX 23

The *E. coli* ETEX 23 strain was developed using a recombinant plasmid expressing the entire CS5 operon

[REDACTED]

9.4.1.4 Inactivated *E. coli* ETEX 24

The *E. coli* ETEX 24 strain was developed using a recombinant plasmid expressing the entire CS6 operon

[REDACTED]

9.4.1.5 LCTBA protein

LCTBA is a hybrid protein between the B-subunit of the *E. coli* heat-labile enterotoxin (LTB) and the B-subunit of the cholera toxin (CTB).

[REDACTED]

9.4.1.6 Oral dmLT adjuvant

LT(R192G/L211A), or dmLT is a derivative of wild-type enterotoxigenic *E. coli* heat-labile enterotoxin that has been genetically modified by replacing the arginine at amino acid position 192 with glycine and the leucine at amino acid position 211 with alanine [25].

[REDACTED]

The protein dmLT has been manufactured under cGMP at [REDACTED]. In addition, the stability testing of this clinical lot of dmLT will continue over the course of the clinical phase of this Phase II trial.

9.4.1.7 Sodium bicarbonate protective buffer powder [REDACTED] used in the Wet formulation Protective buffer is used to neutralize gastric acidity upon ingestion of vaccine. The dried powder is supplied in moisture-proof sachets (5.6 g/sachet).

For use, the carbonate buffer is dissolved in 150 ml of potable water. The Sodium hydrogen carbonate buffer has been produced by [REDACTED].

9.4.1.8 dmLT LCTBA spray-dried preparation

The dmLT spray-dried preparation was produced under GMP at [REDACTED].

9.4.1.9 dmLT LCTBA spray-dried powder together with effervescent powder and excipients.

The complete dmLT/LCTBA effervescent powder was produced under GMP at [REDACTED]

Protective buffer is used to neutralize gastric acidity upon ingestion of vaccine in particular to protect the dmLT against degradation. The dried powder is supplied in moisture-proof sachets (10.84 g/sachet).

For use, the carbonate buffer is dissolved in 150 ml of potable water.

